- To assess the feasibility of the implementation of the triage and treat approach in routine care

¹ All currently available Nucleic Acid Amplification Tests for drug-resistance detection Positive sputum samples will be screened using Xpert XDR assay until we meet the recruitment target for cohort 2. Thereafter, only RR-TB patients will be screened for cohort 1. Xpert XDR detects resistance to INH, Fluoroquinolones and 2nd Line Injectables

² All eligible patients will provide an additional sputum sample for Xpert XDR testing at screening, if reflex testing on provided sputum sample is not feasible

³ Phenotypic DST to BDQ, Linezolid and Clofazimine will be offered for pre-XDR TB cases as per in-country guidelines

⁴ Choice of regimen will be guided by best available evidence from clinical trials using novel regimen, current WHO and in-country guidelines as described in Table 2

⁵ Primary outcome measures for cohort 1 will be compared to a historical dataset of DR-TB patients diagnosed and treated at the each of the facilities over the last 2 years (approximately 24 months)

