2.4. Potential Benefits

There will be a direct benefit to patients who participate in this study. Participants will have access to novel drugs, diagnostics and improved treatment monitoring, not otherwise available through standard of care practice. We believe that the diagnostic methods and drugs used in this study could significantly improve TB treatment outcomes. Additionally, a rapid diagnosis coupled with initiation of appropriate treatment could potentially reduce the number of participants that are lost in the care cascade during this period. Generating evidence through implementation research on the feasibility, acceptability and cost effectiveness of novel diagnostics in improving DR-TB outcomes will fast-track translation of these study findings into policy and practice for maximum public health benefit. Given the development of the novel tests and the importance of the public health approach in triaging DR-TB participants to suitable all-oral regimens, a study evaluating the strategy is warranted. Finally, given the delays in DR-TB diagnosis, and appropriate treatment initiation, high toxicity of drugs in use, identifying strategies to improve DR-TB outcomes are important to the success of TB programmes globally.

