6.2.3. Selection of Historical Cohorts

Each CRS will build a dataset of historical RR-TB participants that were diagnosed and started on treatment within 12 - 18 months prior to starting enrolment of the study at each of the clinical research sites. Clinical and laboratory data from this retrospective cohort will be obtained from treatment registers, participant charts and laboratory databases at each of the clinical research sites. The following data variables will be extracted: date of birth, or age, sex, HIV and ART status, facility or clinic, year and month of treatment, type of DR-TB, certainty of diagnosis (confirmed by DST or presumed, i.e., contact of DR-TB source case or failing adherent first-line TB treatment), disease classification, treatment start date and any bacteriological results on treatment (date, mycobacterial culture, DST and genotypic results), where relevant. Data on all drugs from previous DR-TB treatment regimen, DR-TB Outcomes: cure, completion, default, death, loss to follow up (LTFU) will be abstracted. Historical data will be collected on specially designed case report forms (CRF) and will be subject to routine quality assurance/control QA/QC of data to ensure maximum quality. Bias by time period and by other confounders such as HIV, gender and age, will be controlled for in the analysis. No historical data will be generated for cohort 2, as no routine data on HR-TB is available.

6.3. Participant Inclusion Criteria for cohorts 1 and 2

1. Ambulant adults \geq 18 years of age
2. Newly diagnosed PTB patients receiving less than 5 days of treatment since new diagnosis:
 - a) Cohort 1: < 5 days of DR-TB treatment
 - b) Cohort 2: < 5 days of INH mono-resistant TB treatment preceding study entry for the current TB episode, or
3. Sputum positive (smear and or culture) TB patients classified as failing first line treatment
4. Any currently available Nucleic Acid Amplification Tests for drug-resistance detection changes/assay positive for M.tb infection with:
Cohort 1: at least Rifampicin resistance

- Cohort 2: Rifampicin susceptible co-occurring with INH, fluoroquinolone, ethionamide or aminoglycoside resistance (detected by Xpert XDR) occurring alone or in combination
5. Capacity to provide informed consent
 6. HIV infected and uninfected participants are allowed in the study. Participants already on ART will be allowed in the study provided the ART regimen in use has no contraindications to the proposed TB drug regimen

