- g. Optional Storage Consent for additional sampling collection and storage: Subset of participants who are willing to consent to provision of urine and blood samples at enrolment, month 3, the end of TB treatment, and 6 months post treatment completion if still in follow up, will be required to provide written consent

- h. **Optional Blood Sampling:** # Subset of participants to provide samples to be collected at enrolment, month 3, at the end of TB treatment, and 6 months post treatment completion if participant still in follow up
- i. **Optional Spot Urine Collection Sample:** **Subset of participants to provide** pre-treatment spot urine collection to be conducted during the enrolment visit
- j. **Optional Self-collection of Urine Sample:** **Subset of** participants to collect a 24-hour urine sample following first dose of TB treatment and another 24-hour self-collection urine sample at month 6 after treatment initiation
- k. **Participant Questionnaire:** assess participant associated costs and acceptability of study approach; schedule for administration to be finalised with sub-study protocol
 - I. **Reporting of adverse events:** record solicited grade 3 and 4 adverse events during treatment phase only and all serious adverse events throughout study follow-up.

Table 4 : Schedule of Evaluation for Drug-Resistant Tuberculosis participants in the TRiAD Study Cohort 2

Visit	Screening	Enrolment	Treatment and Follow Up Period ^a											
			Week 2	Month 1	Month 2	Month 3	Month 4	Month 5	Month 6	Month 9	Month 12	Month 15		
Time of visit														
Inclusion/Exclusion Criteria	X	X												
Informed Consent	X	X												
Sociodemographic Information		X												
Medical/treatment History		X												
Clinical Exam		X												
TB Symptom Profile		X												
ECG monitoring		X												
Chest X-Ray ^b		X												
Sputum Sampling ^c	X	X		X	X	X	X	X	X	X	X	X		
Telephonic Assessment														

Notes:

- Treatment and follow-up:** Passive follow-up visits up to 6 months post-TB treatment, routine monitoring of treatment response. Passive follow-up visits will collect AE's, SAE's, verification of survival and participant reported TB outcome information. These will be conducted telephonically
- Chest X-Ray:** Will be conducted at screening visit, and thereafter at the request of the treating clinician if deemed necessary. In Nigeria, X-rays will be done at screening visit, month 4 and end of treatment

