9. STATISTICAL CONSIDERATIONS

9.1. Power and Sample size calculations:

The study will be powered based on the two primary endpoints:

- i) Numbers needed to detect a reduced time to resistance-pattern appropriate treatment initiation for all drug-resistant cases compared to the historical cohort; and
- ii) The difference in proportion of favourable treatment outcomes compared to the historical cohort, allowing for stratification by study site (geographical location).

Current data, mainly from South Africa, show a median time to resistance-pattern appropriate treatment initiation for drug-resistant participants between 15 and 46 days (1-3). With an assumption of an anticipated time to treatment initiation of one week in our study (allowing time for providing repeat sputum samples and delays in Xpert testing), 220 RR-TB participants must be enrolled in cohort one in each country (440 in South Africa), to achieve 90% power to show a shortening of time to treatment initiation. This sample size includes an allowance for an overall 15% loss to follow-up.

Table 6: Reported median times (in days [IQR]) to treatment of drug-resistant TB in literature

Patient type	Xpert-based	LPA-based	Phenotypic DST-based	Location/date	Ref	
All	MDR+XDR	17 [9-47]	38 [23-54]	81 (49-115)	Johannesburg, South Africa 2017	(34)
	RR	0 [0-1]	20 [10-16]	106 [30-124]	Multi-site 2011 (Boehme)	
	MDR	8 [5-25]	50		MSF Cape Town 2015	(35)
	MDR	17 [13-22]	43 [40-46]		Cape Town 2014	(36)
	MDR	15 [1-29]	32 [7-57]		South Africa 2017	(37)

	RR (only 4 pts)	2	21	40 (MGIT)	Cape Town South Africa 2011	
	MDR			88 [29-126]	Korea 2019	(38)
	XDR			97 [79-126]	Korea 2019	(38)
Smear positive	MDR + XDR	15 [1-42]	32 [7-42]	81 [75-107]	Johannesburg, South Africa 2017	
Smear negative	MDR + XDR	-	54 [45-62]	Johannesburg, South Africa	Johannesburg, South Africa 2017	

For the proportion of favourable study outcomes, we used the most recent treatment completion proportions of Kwazulu-Natal province of South Africa, including one of the study sites (4). The average MDR-TB treatment completion proportion is 63%, varying from 57% in their long regimen to 74% using a bedaquiline-based short regimen. The study sample size of n=220 per study site as calculated above will be sufficient to detect an improvement in treatment outcomes with a minimum difference from 74% to 85% (80% power; larger differences with 90% power [from baseline success of 71% and less]), also allowing for 15% loss to follow-up.

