The estimated XDR prevalence among MDR cases is 4.3% in South Africa (2018 Global TB report), 0.6% and 0.7% in Nigeria and Ethiopia (2019 Global TB report). This would mean that N=880*4.3% = 38 XDR cases. As BPaL eligibility extends to pre-XDR patients and treatment intolerant MDR patients, it is expected that a higher number will be on BPaL. A total of 40 participants (including 15% LFU) are needed to detect an improvement from 53% to 85%. This number should be possible for all sites together. Assuming approx. 10% HR-TB in each site, we aim to enrol N=400 in cohort 2 which would allow for approximately 100 HR-TB participants per site, which should be sufficient for studying associated secondary study outcomes.

9.2. Analysis including statistical methods:

Primary endpoint analysis:

- The time to appropriate treatment initiation will be calculated as median days (with interquartile range) between the first sputum collection date and the date of start of the regimen appropriate to the drug resistance pattern (defined as drug-resistance pattern appropriate treatment). This will be compared to the same time in the historical cohort and stratified by geographical location (study site). Confounding will be addressed by multivariable analysis.
- The proportion of favourable study outcomes [treatment cure or completion, based on the WHO definitions (5) will be calculated in the overall study population of cohort 1, and compared with the same proportion in the historical cohort, and stratified by geographical location (study site). In a secondary analysis, these proportions will also be calculated per type of DR-TB. Confounding will be addressed by multivariable analysis.

Both of these outcomes will only be calculated in the primary cohort (cohort 1), as no reliable historical data exist for either endpoint for HR-TB (cohort 2).

Secondary endpoint analysis:

- Prevalence of HR-TB stratified by geographical location. This will be calculated in cohort 2 and stratified by HIV status.
- The incidence of adverse events will be divided into adverse events and serious adverse events and calculated in proportions using both cohort 1 and 2. These will also be stratified by type of DR-TB, treatment regimen, and HIV status.
- Feasibility and acceptability (participant and health care provider perspective), stratified by type of DR-TB regimen (cohort 1 and 2)

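### Favourable outcome is computed over everyone enrolled in cohort 1 but compared with a historical cohort of treatment starters only, and the time endpoint cannot show pre-treatment loss in either cohort

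*Protocol*

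**What the plan says.** **Time endpoint.** Section 9.2: "The time to appropriate treatment initiation will be calculated as median days (with interquartile range) between the first sputum collection date" and the date on which the resistance-appropriate regimen starts. "This will be compared to the same time in the historical cohort".

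**Outcome endpoint.** The same section calculates cure or completion over the whole of cohort 1 and compares it with the same proportion in the historical cohort.

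**Historical entry.** Section 6.2.3 describes "historical RR-TB participants that were diagnosed and started on treatment within 12 - 18 months prior to starting enrolment". A footnote to the study schema in section 1 describes a "historical dataset of DR-TB patients diagnosed and treated at the each of the facilities over the last 2 years". The two differ on the time window and should be reconciled, but they agree that a historical patient must have been treated.

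**Cohort 1 entry.** Section 6.3 asks for "Cohort 1: < 5 days of DR-TB treatment", which includes none. Table 3 puts the column for 24 hours after the first dose after the enrolment column, and its notes include an optional "pre-treatment spot urine collection to be conducted during the enrolment visit". Enrolment before the first dose is thus foreseen.

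**Stated benefit.** Section 2.4 says that rapid diagnosis with appropriate treatment "could potentially reduce the number of participants that are lost in the care cascade during this period".

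**The concern.** One cohort is defined by a treatment start and the other by enrolment, which can come earlier. Between enrolment and first dose a cohort 1 participant can die or disappear. Under section 9.2 that person stays in the denominator for favourable outcome and cannot be a success. The historical patient with the same course was never abstracted. The outcome comparison would then mix any effect of the strategy with a difference in who is counted.

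The time endpoint has a different weakness. Someone who never starts has no second date and so contributes nothing to a median of days between two dates, in either cohort. If the strategy reduces loss before treatment, this comparison cannot register it, although the protocol names that reduction as a benefit.

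**Working it through.** **1. Who is counted, endpoint by endpoint**

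| | Historical cohort | Cohort 1 |
|---|---|---|
| Lost or dead before the point of enrolment | absent (no start) | absent (never consented) |
| Lost or dead between enrolment and first dose | absent (no start) | enrolled |
| Enters favourable-outcome denominator if never started | no | yes, as section 9.2 is worded |
| Enters median time if never started | no | no (no second date) |

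The cohorts differ only in the second row, and that difference reaches only the outcome endpoint.

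**2. The plan's own outcome figure.** Section 9.1 gives 74% against 85%, n = 220, 80% power. Assume two-sided alpha 0.05, which section 9.1 does not state, and 220 in each group. With p̄ = (p1 + p2)/2,

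power = Φ{ [ (p2 − p1)√n − 1.96√(2p̄(1 − p̄)) ] / √(p1(1 − p1) + p2(1 − p2)) }.

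For p1 = 0.74, p2 = 0.85, n = 220: (1.632 − 1.119)/0.566 = 0.906, so power is 81.8%. With 15% lost from both groups (n = 187) it is 75.2%. The stated 80% is therefore reproduced only if the loss is not taken from both groups. The present point does not depend on this.

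**3. Effect of never-starters on cohort 1.** Let r be the share of cohort 1 enrolees who never start. The protocol gives no r, so these values are assumptions. Success over all enrolees = 0.85 × (1 − r); the historical 74% is unchanged because it contains starters only. Power uses the formula in step 2 with n = 220 per group.

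| r | Never-starters per 220 | Cohort 1 success | Difference from 74% | Power |
|---|---|---|---|---|
| 0 | 0 | 85.0% | 11.0 points | 82% |
| 1% | about 2 | 84.2% | 10.2 points | 75% |
| 3% | about 7 | 82.5% | 8.5 points | 57% |
| 5% | 11 | 80.8% | 6.8 points | 39% |

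The planned difference would vanish at r = 1 − 0.74/0.85 = 12.9%.

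**4. What the time endpoint leaves out.** If a share q of all diagnosed patients never starts, the median over all diagnosed is the starters' quantile at 0.5/(1 − q). With exponential times (an assumption) the starters' median is multiplied by −ln(1 − 0.5/(1 − q))/ln 2, which is 1.08 for q = 5% and 1.42 for q = 20%. Take 15 days for the historical period, the lower end of the range in section 9.1, where data "show a median time to resistance-pattern appropriate treatment initiation for drug-resistant participants between 15 and 46 days", and the anticipated 7 days for the study. If q fell from 20% to 5%, the medians over all diagnosed would be 21.2 and 7.5 days, 13.7 days apart. The starters' medians would still be 15 and 7 days, 8 apart, just as if q had not changed. The values of q are illustrative. This step shows what a starters-only median cannot see; it does not measure a bias between the cohorts.

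**The case against.** **Table 7 presupposes treatment.** Its title refers to treated participants, death is defined as death during treatment, and loss to follow-up as interrupted treatment. Section 6.2.1 times follow-up from treatment initiation. On that reading a never-starter has no outcome and would fall out. This is a fair reading, but section 9.2 names the whole cohort as the denominator, and the not-evaluated category could hold such a person. The text supports both readings, so the denominator has to be stated.

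**The exposed window is probably short.** Cohort 1 participants are ambulant, have been contacted and have consented, and some have already begun treatment. This stands: r may be small.

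**The error is conservative.** It lowers cohort 1 success only, so it cannot produce a false claim of benefit. This also stands. The cost is an understated effect and lost power.

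**An analysis plan could settle it.** For the denominator it could. It could not add historical patients whom section 6.2.3 excludes from abstraction, and this protocol already fixes both the entry rule and the denominator.

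**Stronger readings that a reader might infer.** One is that the two time medians have different denominators. They do not: if non-starters have no second date, both medians use starters. Another is that a historical non-start rate of 10%, 20% or 30%, which would turn 74% success among starters into 67%, 59% or 52% of all diagnosed, measures the bias. It does not: that is the gap between starters and all diagnosed within the historical period, and cohort 1 also lacks those lost or dead before consent.

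**Conclusion.** The point holds for the favourable-outcome endpoint as section 9.2 is worded: all cohort 1 enrolees are set against historical starters. The direction is against the intervention. The size is 0.85 × r, so about 0.9 points at r = 1% and 2.6 points at r = 3%, where r is unknown and may be small. This rests on never-starters being kept in the denominator as not favourable and on 85% being the success among starters. Even a few never-starters would cost noticeable power at 220 per group.

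For the time endpoint the point is narrower. Both medians condition on starting, so the comparison is aligned in that respect but cannot show the reduction in pre-treatment loss named in section 2.4. The documents do not support a claim that the time comparison is biased by unequal denominators, or that the design favours the intervention through this route.

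**What to change.** In section 9.2, define the primary comparison of both endpoints among participants who started DR-TB treatment, in both cohorts. This matches the existing historical entry rule and the title of Table 7. Report separately the number and proportion of cohort 1 enrolees who never started, with deaths and losses before start, and add a sensitivity analysis of favourable outcome over all cohort 1 enrolees. A person who started DR-TB treatment but never the appropriate regimen still has no end date for the time endpoint; whatever rule is adopted must be the same in both cohorts.

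A historical cohort of all RR-TB diagnoses, analysed by cumulative incidence with death or loss before start as a competing event, is sound only if the study period is also counted from all laboratory RR-TB diagnoses. Section 6.6 already foresees using laboratory records to contact all newly identified RR-TB patients. Setting all historical diagnoses against consented participants would put pre-consent deaths and losses in the control only and could create a false benefit.

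The cost of the main change is a few sentences and one extra table, with no new historical abstraction. The downside is that the primary comparison does not capture pre-treatment loss, which is then only described.

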1. STUDY SUMMARY

The TRiAD study is a multi-center, multi-country Prospective Pragmatic Cohort study assessing the effectiveness, feasibility, acceptability, and cost-effectiveness of implementing the Xpert MTB/XDR (Xpert XDR; Cepheid) assay for rapid triage-and-treatment with short, all-oral drug resistant tuberculosis (DR-TB) treatment. The proposed study aims to screen approximately 4800 GeneXpert MTB/RIF or Ultra MTB-positive participants or any currently available Nucleic Acid Amplification Tests for drug-resistance detection changes (irrespective of rifampicin resistance status) from clinical research sites in South Africa, Nigeria and Ethiopia to enrol 880 rifampicin resistant (RR) and 400 rifampicin sensitive and isoniazid, fluroquinolone and or second line injectable drug (SLID) resistant participants over a period of 12-18 months. The Xpert XDR assay, a rapid genotypic test, will be implemented as a reflex test to detect resistance to isoniazid, fluoroquinolones and second-line injectable agents to provide rapid genotypic susceptibility testing for DR-TB detection. Participants that test positive for *Mycobacterium tuberculosis* (*M.tb*) with rifampicin resistance will be enrolled in *Cohort 1* (n=880). Participants that test positive for *M.tb* that are rifampicin susceptible with isoniazid, fluroquinolone and or second line injectable drug (SLID) resistant will be enrolled in *Cohort 2* (n=400). Results from the Xpert XDR assay will be used to guide selection of appropriate, evidence-based, all-oral DR-TB treatment regimens of shortest possible duration. The tuberculosis molecular bacterial load assay (TB-MBLA) will be used as an adjunct to provide bacillary load monitoring over the course of treatment to assess real-time treatment response. Operational research will provide information about the feasibility, acceptability and cost-effectiveness to inform policies and guidelines for programmatic implementation of the triage-and-treat model.

[figure not shown]
Table 1 Overview of TRiAD Study

Study Aim	To evaluate the effectiveness, operational feasibility, acceptability, and cost-effectiveness of implementing the Xpert MTB/XDR assay for rapid triage and selection of all-oral regimens for Drug-Resistant Tuberculosis (DR-TB)
Study Design	Prospective Pragmatic Cohort Study: non-randomized interventional phase 4 (clinical access protocol) implementation science study utilizing interventions of proven clinical efficacy

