3. DEFINITIONS OF DR-TB

- HR-TB is defined as resistance to at least isoniazid without rifampicin resistance
- RR-TB is defined as resistance to at least rifampicin without isoniazid resistance

Definitions of MDR-TB, pre-XDR and XDR-TB in background sections of this protocol refer to old WHO definitions:

- MDR-TB; resistance to at least rifampicin and isoniazid
- Pre XDR-TB; strains that fulfil the definition of MDR-TB with additional resistance to the aminoglycosides or fluoroquinolones
- XDR-TB; strains that fulfil the definition of MDR-TB with additional resistance to the aminoglycosides and fluoroquinolones.

For the purpose of defining DR-TB categories in the current study we will utilise updated 2021 WHO definitions to categorise pre-XDR-TB and XDR-TB (32)

- Pre-XDR TB; strains that fulfil the definition of RR-TB/MDR-TB with additional resistance to any fluoroquinolone
- XDR-TB; strains that fulfil the definition of RR-TB/MDR-TB with additional resistance to any fluoroquinolone and at least one additional group A drug (BDQ or LZD).

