4.5. Study Outcome Measures

Primary Outcomes:

- Time to initiation of resistance-pattern appropriate TB treatment from the date of first sputum collection
- Proportion of participants with favourable treatment outcome as defined in section 9.3

Secondary Outcomes:

- Incidence of adverse drug reactions documented during all-oral treatment under operational conditions (cohort 1 and 2)
- All-cause mortality for the duration of treatment and follow-up (cohort 1 and 2)
- Time to sputum (culture) conversion (cohort 1 and 2)
- Prevalence of HR-TB (cohort 1)
- Prevalence of XDR-TB (cohort 2)
- Proportion of participants with BDQ and LZD resistance not eligible for short-course treatment
- Clinical utility and feasibility of TB-MBLA for bacteriological follow-up in DR-TB treatment (assessment of viable bacterial load trajectories in response to treatment) (cohort 1)
- Accuracy and quality of Xpert XDR testing (cohort 1 and 2)
- Additional resistance to new and repurposed drugs (cohort 1 and cohort 2)
- Cost effectiveness (cost per person tested and incremental cost per DR-TB participant timely initiated on appropriate treatment) (cohort 1 and 2)
- Feasibility and acceptability of participant triaging (participant, health care provider and policy makers' perspective) with enablers and barriers for implementing the algorithm (cohort 1 and 2)
- Operational feasibility of Xpert XDR testing (infrastructure and human resource requirements) (cohort 1 and 2)

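### Sections 4.5 and 9.2 name different cohorts for HR-TB prevalence, and neither cohort yields one; 4.5 also places XDR-TB prevalence in the rifampicin-susceptible cohort

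*Protocol*

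**What the plan says.** The microbiological objectives in section 4.4.2 include the prevalence of HR-TB by geographic location and the prevalence of pre-XDR and XDR-TB. They name no cohort.

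Section 4.5 does name cohorts: "Prevalence of HR-TB (cohort 1" for the first and "Prevalence of XDR-TB (cohort 2" for XDR-TB. Section 9.2 gives a different cohort for HR-TB: "Prevalence of HR-TB stratified by geographical location. This will be calculated in cohort 2 and stratified by HIV status".

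For the definitions, section 3 states: "HR-TB is defined as resistance to at least isoniazid without rifampicin resistance". It builds XDR-TB on RR-TB or MDR-TB, so XDR-TB requires rifampicin resistance. Section 6.3 admits people to cohort 1 with at least rifampicin resistance. It admits people to cohort 2 if they are rifampicin susceptible and Xpert XDR has found resistance to isoniazid, a fluoroquinolone, ethionamide or an aminoglycoside, alone or together. Section 6.2.2 nevertheless describes all 400 of cohort 2 as HR, with country targets of 200, 100 and 100.

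On screening, section 1 plans to "screen approximately 4800 GeneXpert MTB/RIF or Ultra MTB-positive participants", whatever their rifampicin status. Note 1 to the study schema adds: "Positive sputum samples will be screened using Xpert XDR assay until we meet the recruitment target for cohort 2". After that point only RR-TB patients are screened. Section 9.1 gives the planning assumption: "Assuming approx. 10% HR-TB in each site, we aim to enrol N=400 in cohort 2".

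**The concern.** A prevalence needs a denominator that was not chosen on the condition being counted. Cohort 1 excludes HR-TB by definition. Cohort 2 is selected on resistance, so it holds cases and almost nothing else. The two sections also contradict each other, so an analyst cannot follow both.

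At stake is a stated secondary objective. Section 6.2.3 says that no routine HR-TB data are available, so this estimate could not be replaced from programme records. The right denominator has to be recorded while universal testing is still open, because people who are screened and not enrolled are hard to recover later.

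**Working it through.** **Step 1. Section 4.5 as written.** Inputs: the section 3 definitions, the section 6.3 entry criteria, and cohort sizes of 880 and 400.

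| Outcome | Cohort named | Cohort's rifampicin status | Status the definition requires | Result |
|---|---|---|---|---|
| HR-TB | 1 | resistant | not resistant | 0/880 = 0% |
| XDR-TB | 2 | susceptible | resistant | 0/400 = 0% |

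The two labels look transposed. Section 9.1 counts its expected XDR cases within the 880 of cohort 1 ("This would mean that N=880*4.3% = 38 XDR cases"). That sentence is used here only to show which cohort the authors had in mind.

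**Step 2. Swap the labels.** XDR-TB then sits in the rifampicin-resistant cohort, and HR-TB agrees with section 9.2. It remains to ask whether cohort 2 can give HR-TB prevalence.

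**Step 3. HR-TB within cohort 2.** If all members are HR, as section 6.2.2 says, the result is 400/400 = 100% at every location, whatever the true prevalence.

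If other resistance calls also enter, as section 6.3 allows, let p be the true HR-TB prevalence among rifampicin-susceptible people. Let q be the proportion with a call for another drug, taken as independent of isoniazid resistance. The protocol gives no q, so the values below are assumptions. The isoniazid share of cohort 2 is p / [p + (1 − p)q].

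| p | q | Calculation | Share |
|---|---|---|---|
| 10% | 0 | 0.10 / 0.10 | 100% |
| 10% | 1% | 0.10 / (0.10 + 0.009) | 92% |
| 10% | 5% | 0.10 / (0.10 + 0.045) | 69% |
| 5% | 1% | 0.05 / (0.05 + 0.0095) | 84% |
| 20% | 1% | 0.20 / (0.20 + 0.008) | 96% |

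At q = 1%, a fourfold range in true prevalence (5% to 20%) shrinks to 84% to 96%. Stratifying by location then says little about prevalence.

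**Step 4. Cohort 2 as numerator over people screened.** Screening runs to a case target, so the number screened varies with prevalence. For 400 cases it is 400/0.05 = 8000, 400/0.10 = 4000 or 400/0.20 = 2000 rifampicin-susceptible people. Cases over people screened is therefore informative.

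The remaining fault is that enrolled cases leave out HR-TB people who decline or are excluded under section 6.4. If a fraction f of HR-TB people enrol, a true 10% appears as 0.10 × f: 7% at f = 0.7 and 10% at f = 1.0. The range for f is assumed.

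**Step 5. Precision with the screened denominator.** At 10%, the country targets imply 200/0.10 = 2000 rifampicin-susceptible people in South Africa and 100/0.10 = 1000 in each other country. Approximate 95% half-widths are 1.96 × √(0.09/2000) = 1.3 points and 1.96 × √(0.09/1000) = 1.9 points, before any allowance for clustering by site.

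**The case against.** The strongest reply is that this amounts to two transposed labels and an unnamed denominator for a descriptive secondary outcome. On that view, cohort 2 in section 9.2 means only the source of cases, and an analysis plan would supply the rest.

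Part of this stands. The XDR-TB error is a labelling slip. Cohort 2 cases over people screened would be a usable estimate apart from non-enrolment. The outcome is stratified by location, and no formal comparison of locations is promised.

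The reply does not remove the HR-TB problem. Section 9.2 is not silent: it names a population for the calculation, and that population cannot give the objective in section 4.4.2. An analysis plan that followed it would carry the error forward. The screening descriptions in section 1, the schema note and section 6.2 do not identify a rifampicin-susceptible denominator either.

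Three stronger readings are tempting and should be avoided:

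- A reader might infer that any ratio built on 400 cases is fixed by the recruitment target. It is not, because the number screened is free to vary and the 4800 is only approximate.
- A reader might infer that the 10% in section 9.1 proves which denominator was meant. It does not. 10% × (4800 − 880) = 392, close to 400, but 10% × 4800 = 480 would also yield 400 enrolled at 83% uptake (400/480). The protocol states neither derivation.
- A reader might set 0% in cohort 2 against 4.3% in cohort 1 as the size of the XDR-TB error. The 4.3% is the South African rate applied to all 880. The country rates in section 9.1 give 440 × 4.3% + 220 × 0.6% + 220 × 0.7% = about 22 cases. The labelling error stands without any forecast.

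**Conclusion.** The protocol contradicts itself on where HR-TB prevalence is calculated, and neither cohort can give it. Section 4.5 leads to 0% for HR-TB and 0% for XDR-TB. Section 9.2 leads to 100% for HR-TB if section 6.2.2 describes cohort 2 correctly, and otherwise to an isoniazid share of resistance calls. The zeros and the 100% follow from the definitions and entry criteria alone. The intermediate values (69% to 96%) and the 7% to 10% range for enrolled cases rest on assumed rates.

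A reader might infer that the primary comparison or the sample size is compromised. The documents do not support that: both primary endpoints are analysed in cohort 1 against the historical cohort and use neither prevalence. The correction should be made, but its reach is limited to secondary outcomes.

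**What to change.** In section 4.5, move XDR-TB prevalence, together with pre-XDR-TB, to the RR-TB population and remove HR-TB prevalence from cohort 1.

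In sections 4.5 and 9.2, define HR-TB prevalence as follows:

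- **Numerator:** people with isoniazid resistance on Xpert XDR among those in the denominator.
- **Denominator:** all rifampicin-susceptible, M.tb-positive people with a valid Xpert XDR result at screening, enrolled or not.
- **Strata and period:** by location, counted at each site or country until testing of all M.tb-positive samples stops there. The cohort 2 targets are set by country, so one common closing date may not fit.

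Keep a short screening log: date, site, rifampicin result, Xpert XDR result and its validity.

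State whether people excluded under section 6.4 or 6.5 for bedaquiline or linezolid resistance count in XDR-TB prevalence. Reconcile those sections with 4.4.2 and 4.5, which report such resistance as an objective and an outcome.

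The cost is rewording and the log. Screening already has its own written consent (section 7.1), and the log also serves the indeterminate rate and the cost per person tested in section 9.2. The downside concerns HIV. Table 4 places medical history at enrolment, so prevalence by HIV status needs HIV status at screening. Otherwise that stratification is limited to describing enrolled participants, or is dropped.
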